### 4.3 Withdrawal Criteria

Participation of a patient in this clinical study may be discontinued for any of the following reasons:

- The patient withdraws consent or requests discontinuation from the study for any reason
- Occurrence of any medical condition or circumstance that exposes the patient to substantial risk and/or does not allow the patient to adhere to the requirements of the protocol
- Any serious adverse event (SAE), clinically significant adverse event, severe laboratory abnormality (including meeting any of the suspected drug-induced liver injury criteria as described in the Drug-Induced Liver Injury Monitoring Plan in Appendix E), intercurrent illness, or other medical condition that is considered related to the study drug or indicates to the Investigator that continued participation is not in the best interest of the patient
- Pregnancy
- Requirement of prohibited concomitant medication after consultation with the Medical Monitor
- Patient failure to comply with protocol requirements or study-related procedures
- Termination of the study by the Sponsor or the regulatory authority

If a patient withdraws prematurely from the study due to the above criteria or any other reason, study staff should make every effort to complete the full panel of assessments scheduled for the End of Treatment Visit (Visit 9, Week 52). The reason for patient withdrawal must be documented in the electronic case report form (eCRF).

In the case of patients lost to follow-up, attempts to contact the patient must be made and documented in the patient's medical records. A minimum of 3 attempts to contact the patient must be made and documented prior to declaring the patient lost to follow-up.

Withdrawn patients will not be replaced.

#### 5 STUDY TREATMENTS

# 5.1 Treatment Groups

Approximately 264 eligible patients with NASH will be randomized into 1 of 3 parallel treatment groups (stratified by biopsy fibrosis score), each of which will contain approximately 88 patients, as outlined in Table 3.

Table 3. Study Treatment Groups and Dosing Regimens

Treatment Group	Dosing Regimen [1]						
Group 1: 300 mg NST-4016 1 capsule (300 mg) NST-4016 and 1 capsule matching place							
Group 2: 600 mg NST-4016 2 capsules (300 mg each) NST-4016							
Group 3: placebo	2 capsules matching placebo						
1. Patients will take 2 capsules in the morning with water once daily (at approximately the same time each day) for							
52 weeks. Study drug can be taken in the fed or fasted state.							

## 5.2 Rationale for Dosing

The maximum dose selected for this study (600 mg) was previously administered for 12 weeks daily in patients with hypertriglyceridemia or mixed dyslipidemia and demonstrated statistically significant and clinically meaningful reductions in triglycerides and cholesterol and was shown to be safe and well tolerated. Single ascending doses >600 mg (up to 2800 mg) resulted in increasing gastrointestinal side effects, which were mainly mild. The low dose selected for this study (300 mg) demonstrated significant reductions in triglycerides and cholesterol, although not as notable as the effects seen with 600 mg dosing. These 2 doses are expected to provide evidence of a dose-response relationship in patients with NASH. Once-daily dosing is consistent with the sustained PD effects seen on lipids in repeat-dose studies.

### 5.3 Randomization and Blinding

This study follows a randomized, double-blind, placebo-controlled design. Patients will be randomized via the Interactive Response Technology (IRT) system to 1 of 3 parallel treatment groups at Visit 2 (Week 0) in a 1:1:1 ratio. Patients will be stratified by biopsy fibrosis score (2 levels: F1 versus F2 or F3). Randomization information will be concealed from the Investigators and the patients until the end of the study, with the exception of an emergency situation involving a patient that requires unblinding of the treatment assignment.

Both NST-4016 and placebo will be provided as capsules for oral administration and will be identical in appearance.

#### 5.4 Breaking the Blind

Until formal conclusion of the study, patients, Investigators, and all site study personnel will remain blinded to treatment allocation, except in the event of a medical emergency that necessitates unblinding. In the event of a medical emergency where knowledge of the patient's treatment assignment would influence the patient's clinical care, the site will be able to unblind the patient via the IRT system. The site should consult the study Medical Monitor prior to unblinding if at all possible without putting the patient's safety at risk. In the case of unblinding, the IRT system will send a blinded notification to study team members to let them know that a patient was unblinded.

# 5.5 Drug Supplies

# 5.5.1 Formulation and Packaging

The drug product is presented as red, oblong-shaped, soft gelatin capsules. The formulation is designed as 300 mg icosabutate (drug substance) in Self-Emulsifying Drug Delivery System (SEDDS). In general, a SEDDS formulation is a mixture of oils and surfactants, which emulsify in aqueous media under conditions of gentle agitation and digestive motility that would be encountered in the stomach and gastrointestinal tract. The use of a self-emulsifying formulation is proposed to increase the bioavailability of drugs with poor water solubility. The formulation contains 300 mg icosabutate formulated in polysorbate 20 and triglycerides medium-chain, with 3-tert-butyl-4-hydroxyanisole added in order to prevent oxidation of the drug substance.

The production of the capsules is carried out under nitrogen. The capsules are packaged as bulk in double polyethylene bags inside a cardboard box. The soft gelatin capsules are packed for patients in high-density polyethylene bottles with a tamper-proof polypropylene screw cap.

## 5.5.2 Study Drug Preparation and Dispensing

Study drug will be dispensed as 300 mg capsules for oral administration at Visits 2 to 8 by blinded site personnel. Patients will receive enough study drug to last until the next study visit.

This study protocol includes contingency measures to manage disruptions due to COVID-19 control measures, including modifications to study drug dispensation specific to situations where COVID-19 is impacting study conduct. See Appendix G for details of COVID-19 contingency measures. In the absence of a COVID-19 impact, it is expected that Investigators and patients follow the protocol requirements as set forth.

## 5.5.3 Study Drug Administration

All patients will take 2 capsules of study drug (either 300 mg NST-4016 and/or matching placebo) orally in the morning with water once daily for 52 weeks. In the event that the Visit 9 biopsy is delayed, patients will continue to administer study drug daily until the biopsy occurs, for up to 30 days after the originally projected Visit 9 date.

Patients should take study drug at approximately the same time each day. Study drug can be taken in the fed or fasted state.

On study visit days, patients should take their daily dose of study drug at the clinical site to accommodate predose trough PK sampling.

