Study drug dosing will begin at Visit 2 (Week 0, Day 0) and will continue daily for 52 weeks. During the 52-week treatment period, patients will return to the clinic for study visits every 1 to 3 months. The following assessments will occur at every study visit during the treatment period: adverse events, concomitant medications, body weight, vital signs, physical examinations, laboratory evaluations (hematology, biochemistry, coagulation, and lipid panels and urinalysis), and trough PK sampling. For a subset of patients (approximately 8 patients per group) at pre-identified sites, blood samples for analysis of additional PK parameters will also be collected predose and up to 24 hours postdose at Visit 2. In addition, hepatic imaging will be performed at Visit 5 (after 16 weeks of treatment) and Visit 9 (after 52 weeks of treatment).

Evaluation of liver inflammation and fibrosis biomarkers (Homeostatic Model Assessment for Insulin Resistance [HOMA-IR], hsCRP, Pro-C3, and ELF panel) will be performed at Visits 2, 5, and 9. Twelve-lead ECGs will be performed at Visits 2, 5, 7, and 9, and a liver biopsy will also be performed at Visit 9. Throughout the study, patients will be monitored for suspected drug-induced liver injury.

A Safety Follow-up Visit (Visit 10) will occur 14 days after the last dose of study drug to assess adverse events, concomitant medications, body weight, vital signs, physical examination findings, laboratory parameters, and 12-lead ECGs. Lipid parameters will be monitored throughout the follow-up period and will be managed by the Investigator.

Patients who discontinue early from the study for any reason prior to completion of the treatment period will be requested to return to the clinic for an Early Termination (ET) Visit as soon as possible after their last intake of study drug. Patients who discontinue early from the study for any reason after completion of the treatment period and before the Safety Follow-up Visit will be requested to return to the clinic for an ET Visit as soon as possible and no later than the planned Safety Follow-up Visit.

From screening through follow-up, the total study duration for each patient who completes the entire treatment period will be approximately 62 weeks. For a summary of procedures to be performed at each visit, refer to the Schedule of Procedures in Appendix A.

An external, independent DSMC will review all available unblinded preliminary safety and biomarker results per the DSMC Charter.

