## 5.5.5 Storage and Accountability

The study drug should be stored refrigerated at 2°C to 8°C for up to 18 months and protected from light. The study drug may be kept at room temperature (not exceeding 25°C) by the patients between study visits for a maximum of 3 months. In case of longer excursions at 15°C to 25°C, the study drug should not be used but returned to site for replacement with new study drug. The study drug must not be frozen.

At the completion of the study, all used and unused supplies should be accounted for, and any unused study drug should be returned to the clinical site for destruction or for return to the distribution site (or designee) for destruction.

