## 6.3.8 Visit 9 (Week 52)

The following procedures will be performed at Visit 9 (Week 52):

- Record concomitant medications.
- Measure body weight.
- Perform complete physical examination.

- Collect vital signs (blood pressure [3 readings], pulse rate, and body temperature) with the patient in the sitting position after 5 minutes of rest and before any blood draws.
- Collect fasting blood sample for the following:
  - o Hematology, biochemistry, coagulation, and lipid panels.
  - o Lipoprotein particle size.
  - o Biomarkers (HOMA-IR, hsCRP, Pro-C3, and ELF panel).
  - o Lipidomic analyses (in a subgroup of patients).
- Collect urine sample for the following:
  - o Urinalysis.
  - o Urine pregnancy test (only for women of childbearing potential).
- Perform 12-lead ECG after the patient has been resting in the supine position for at least 10 minutes.
- Perform MRI-PDFF and cT1 imaging.
- Perform liver biopsy for analyses (including lipidomics in a subset of patients).
- Assess adverse events.
- Collect a PK blood sample.
- Collect returned and used/unused study drug and assess compliance.

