## 6.4 Safety Follow-up Visit (Visit 10, Week 54)

The Safety Follow-up Visit has a visit window of  $\pm 5$  days. The following procedures will be performed at the Safety Follow-up Visit (Visit 10, Week 54):

- Record concomitant medications.
- Measure body weight.
- Perform complete physical examination.
- Collect vital signs (blood pressure [3 readings], pulse rate, and body temperature) with the patient in the sitting position after 5 minutes of rest and before any blood draws.
- Collect fasting blood sample for the following:
  - o Hematology, biochemistry, coagulation, and lipid panels.
  - o Serum pregnancy test (only for women of childbearing potential).
- Collect urine sample for urinalysis.
- Perform 12-lead ECG after the patient has been resting in the supine position for at least 10 minutes.
- Assess adverse events.

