3.1.2 Analysis Visits

Scheduled visits will be assigned to analysis visits as recorded on the electronic case report form (eCRF). Unscheduled and early termination visits will be assigned to analysis visits according to the visit windows described in the following table:

Analysis Visit	Target Analysis Day	Low Analysis Day	High Analysis Day
Visit 2 (Week 0)	1	NA	NA
Visit 3 (Week 4)	28	2	49
Visit 4 (Week 10)	70	50	91
Visit 5 (Week 16)	112	92	140
Visit 6 (Week 24)	168	141	196
Visit 7 (Week 32)	224	197	252
Visit 8 (Week 40)	280	253	322
Visit 9 (Week 52)	364	323	371
Visit 10 (Week 54) Safety FUP	378	372	

If there is more than one assessment within a visit window, then the analysis visit will be assigned by the following priorities:

- 1. Use the assessment from the visit with the matching visit label.
- 2. Use the visit closest to the target visit day; in the case of ties, use the earlier visit.

Further details of analysis visit assignment will be provided in the Analysis Data Model (ADaM) Specifications

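### The dosing extension of up to 30 days for a delayed Visit 9 biopsy was not carried through to drug supply, Visit 10 timing, adverse-event collection or the SAP's visit windows

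*Protocol*

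**What the plan says.** **The extension.** Protocol 5.5.3: "patients will continue to administer study drug daily until the biopsy occurs, for up to 30 days after the originally projected Visit 9 date". Footnote r of Appendix A and SAP 2.2.1 say the same.

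**Supply.** Protocol 5.5.2: "Study drug will be dispensed as 300 mg capsules for oral administration at Visits 2 to 8 by blinded site personnel", and "Patients will receive enough study drug to last until the next study visit". Footnote x of Appendix A agrees. For Visit 9, section 6.3.8 lists "Collect returned and used/unused study drug and assess compliance" but no dispensing and no on-site dose. Extra supply is mentioned only in Appendix G, which is limited to COVID-19 disruption.

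**Visit 10.** Protocol 3.1: "A Safety Follow-up Visit (Visit 10) will occur 14 days after the last dose of study drug". The synopsis agrees, and SAP 2.2.1 gives the same interval as two weeks. Section 6, section 6.4 and Appendix A instead fix the visit at Week 54, Study Day 378, with a window of ±5 days.

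**Safety collection.** Protocol 8.1 collects adverse events up to Visit 10, identified there as Week 54, or the early-termination (ET) visit. Section 8.3 requires serious adverse events to be reported until 30 days after the last dose.

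**Analysis visits.** SAP 3.1.2 takes scheduled visits as labelled on the eCRF and places unscheduled and ET records by day windows. The window for Visit 9 closes on Day 371. The one called "Visit 10 (Week 54) Safety FUP" opens on Day 372 and has no upper limit.

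**The concern.** The extension changes the date of the last dose, and several other rules depend on that date. Those rules were written for dosing that stops at Week 52. For a patient whose biopsy is late, the documents do not say where the extra capsules come from, when the safety visit takes place, or when collection of non-serious adverse events ends. Two sites could follow different sections and both be compliant, one seeing the patient while still on drug and the other two weeks after stopping.

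The safety data for these patients would then mix on-drug and off-drug assessments under one visit name. The fixed day rule in the SAP adds to this for unscheduled and ET records.

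**Working it through.** **Inputs.** Study Days 280, 364 and 378 for Visits 8, 9 and 10, and the ±5-day window for Visit 10 (Appendix A); two capsules daily and the maximum delay of 30 days (5.5.3); Days 371 and 372 (SAP 3.1.2). The projected Visit 9 date is taken as Day 364.

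**1. The plan's own figure.** 364 + 14 = 378, which is Week 54. The two definitions of Visit 10 agree exactly when the last dose is at Week 52.

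**2. Supply.** Visit 8 to Visit 9: 364 − 280 = 84 days, or 84 × 2 = 168 capsules. With the full extension: 394 − 280 = 114 days, or 114 × 2 = 228 capsules. The difference, 228 − 168 = 60 capsules, has no stated source outside Appendix G.

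**3. Visit 10.** For a delay of d days the last dose is on Day 364 + d. The fixed visit is Day 378 (window 373 to 383); the relative visit is Day 378 + d.

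| Delay d | Last dose | Day 378 minus last dose | Relative visit | Days past Day 383 |
|---|---|---|---|---|
| 0 | 364 | +14 | 378 | none |
| 5 | 369 | +9 | 383 | none |
| 14 | 378 | 0 | 392 | 9 |
| 20 | 384 | −6 | 398 | 15 |
| 30 | 394 | −16 | 408 | 25 |

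- The fixed visit precedes the last dose when d > 378 − 364 = 14. At the window edges the thresholds are 373 − 364 = 9 and 383 − 364 = 19.
- At d = 30 the fixed visit falls between 394 − 383 = 11 and 394 − 373 = 21 days before the last dose.
- The relative visit leaves the window once d > 383 − 378 = 5. At d = 30 it is 408 − 383 = 25 days beyond it.

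**4. Adverse events.** On the fixed reading, collection of non-serious events at d = 30 stops 11 to 21 days before dosing does. On the relative reading it runs to Day 408. Serious events are covered to Day 394 + 30 = 424 either way.

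**5. SAP windows.** Once d > 371 − 364 = 7, dosing continues into the follow-up window. At d = 30 the overlap is Days 372 to 394, or 394 − 372 + 1 = 23 days. The protocol counts the first dose as Day 0 and the SAP as Day 1, so on SAP numbering the last dose is Day 395 and the overlap is 24 days. The conclusion is the same.

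**The case against.** The strongest defence is that Visit 9 moves with the biopsy. Section 5.5.3 speaks of an originally projected date, and the biopsy is a Visit 9 procedure. Collection would then fall on the biopsy day. Supplying enough to reach the next visit sets no upper limit, and footnote r is attached to the administration and dispensing row of Appendix A. This stands to the extent that a reader who infers that the extension cannot be carried out goes too far: nothing forbids a larger Visit 8 supply or an unscheduled dispensing. It does not supply the missing step. The dispensing row has no Visit 9 entry, and a Visit 9 moved by up to 30 days leaves its own ±7-day window.

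Four other stronger readings are also unsupported:

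- **Storage.** A single Visit 8 supply stretched to 114 days might seem to breach the rule that "The study drug may be kept at room temperature (not exceeding 25°C) by the patients between study visits for a maximum of 3 months". But section 5.5.5 makes refrigeration the default, for up to 18 months, and provides for replacement after longer room-temperature excursions.
- **Visit 10 always before the last dose.** This happens only on the fixed-calendar reading and only for delays over about 14 days (9 to 19 across the window). Section 3.1, the synopsis and SAP 2.2.1 all place the visit after the last dose.
- **Widespread mislabelling in the SAP.** The day windows apply only to unscheduled and ET records, and within a window the record with the matching visit label takes priority. Treatment-emergent events are defined as after first dose (SAP 3.6.1), with no on-drug and off-drug split. The effect is on by-visit summaries.
- **Damage to the primary endpoint.** If drug ran out at Week 52, the gap to biopsy would be at most 30 days. The SAP accepts biopsies within 90 days of the last dose or Week 52 visit for the mITT Population (3.2.3) and within 30 days of the last dose for the PP Population (3.2.4).

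**Conclusion.** The documents are inconsistent for patients with a delayed Visit 9 biopsy. The conflict between the two Visit 10 anchors is certain from the text and matters most, because it also decides when collection of non-serious adverse events ends. The supply point is an omission: the step is missing, not prohibited. The SAP point is a narrow labelling error with a simple correction.

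The figures quoted are maxima per patient at a 30-day delay, and the problem shrinks with shorter delays: up to 5 days, both anchors still fit the Week 54 window. The documents do not say how many biopsies were or will be delayed, so no effect on the trial's overall results can be stated. SAP 2.2.1 describes the extension in the past tense, but that does not show how the drug was supplied or when Visit 10 took place.

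**What to change.** **Protocol.** Reconcile 5.5.2, 5.5.3, 6.3.8, 6.4, 8.1 and Appendix A so that supply, drug collection, Visit 10 timing and the end of adverse-event collection are all consistent with the extension. Section 3.1, the synopsis and SAP 2.2.1 should then carry the same Visit 10 definition. Which dispensing and visit rule to adopt is for the sponsor and its clinical team; this review does not choose one.

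**SAP.** In 3.1.2, separate on-treatment from follow-up records for unscheduled and ET visits by each patient's actual last-dose date, in place of the fixed Day 372.

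**Cost.** A short clarifying amendment and one sentence in the SAP. The SAP change needs no new data, because the last-dose date is already used for exposure in SAP 3.3.7. If study conduct is already complete, the SAP change can still be made before database lock. The study report can then state how extended patients were supplied and when their Visit 10 fell relative to the last dose.

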# 5.5.4 Treatment Compliance

The quantity of study drug dispensed to and returned by the patient will be counted by site personnel and verified by the Clinical Research Associate (CRA) monitoring the study. All discrepancies in drug accountability should be explained and documented (missed dose, lost capsule, overdose, etc). If the patient is not compliant with study drug intake, the Investigator should discuss this with the patient.

If study drug compliance drops below 80% or surpasses 100% at any given time during the treatment period, the Investigator or designee should discuss compliance with the patient and counsel the patient appropriately. Noncompliance includes missed doses in addition to taking the

wrong dose. The Investigator must continually encourage compliance with the study drug and with the study procedures.

## 5.5.5 Storage and Accountability

The study drug should be stored refrigerated at 2°C to 8°C for up to 18 months and protected from light. The study drug may be kept at room temperature (not exceeding 25°C) by the patients between study visits for a maximum of 3 months. In case of longer excursions at 15°C to 25°C, the study drug should not be used but returned to site for replacement with new study drug. The study drug must not be frozen.

At the completion of the study, all used and unused supplies should be accounted for, and any unused study drug should be returned to the clinical site for destruction or for return to the distribution site (or designee) for destruction.

#### 5.6 Prior and Concomitant Medications and/or Procedures

Unless medically warranted, all concomitant medications should remain stable from screening through the Safety Follow-up Visit (Visit 10). Throughout the duration of the study, patients should not introduce changes to their usual diet (including dietary supplements) or lifestyle.

#### 5.6.1 Excluded Medications and/or Procedures

Excluded medications and procedures include the following:

- Any drug known to produce hepatic steatosis, including systemic corticosteroids, methotrexate, tetracycline, amiodarone, tamoxifen, estrogens at doses greater than those used for hormone replacement, anabolic steroids, or valproic acid, for more than 2 weeks in the 6 months prior to screening. Local corticosteroid injection for musculoskeletal disorders is permitted, including epidural corticosteroid administration.
- Vitamin E >400 U/d, pioglitazone, obeticholic acid, or antiobesity drugs within 3 months prior to screening or since the historical liver biopsy (if applicable), whichever is longer.
- CYP3A or CYP2C19 substrates that have a narrow therapeutic index, as exposure may be reduced.
- Strong inhibitors of CYP2C8, CYP2C9, or CYP2C19.
- Bariatric surgery within the past 5 years or bariatric surgery planned to occur during the study.
- Participation in any other investigational drug study within the previous 3 months or 5 half-lives of the last dose of the investigational drug, whichever is longer.

